6.2.2. Randomization numbers

The study population will be made up of 24 patients with low back pain attributable to degenerative disc disease that is refractory to conventional treatment and with integrity of the external annulus fibrosus demonstrated by MR imaging. Of this cohort, 12 patients will be included in the experimental group and another 12 in the control group. Will be assigned to one or the other randomly. It will be carried out by the CRO centrally and at random, attending to the treatment to be administered to each patient (control or experimental). The assignment will be kept in a sealed and identified envelope.

6.3. CONCOMITANT TREATMENTS

Relevant concomitant medications taken by the patient will be recorded in the CRD regularly due to other parallel treatments allowed during the study. If analgesic treatment is necessary, it will preferably be carried out with paracetamol. I know avoid administering corticosteroids or anti-inflammatory therapy if they are not strictly necessary. If necessary, it should be noted in the clinical history and in the CRD (Section "Concomitant Medication").

6.4. ACCOUNTING OF THE DRUG

The product under study or medicine is produced individually by starting from the bone marrow from each donor. In all cases, the MSV will be registered and identified. produced for each patient in the IBGM.

6.5. MANAGEMENT OF STUDY MEDICATION

The study medication, properly packaged MSV in a thermostatic container, was transported immediately after production to the application center. Has a stability longer than 12 hours at room temperature and is given as an injection in the area of the nucleus pulposus of the affected spinal segment.

7. DEVELOPMENT OF THE TEST AND ASSESSMENT OF THE RESPONSE 7.1 ASSESSMENT OF THE RESPONSE

7.1.1. Main evaluation variable

The objective is the evaluation of the efficacy using clinical criteria (Visual evaluation back pain analogue-VAS-, Oswestry disability index -ODI-, quality of life --SF-12--), and imaging (quantitative MRI) at 6 and 12 months after intervention.

7.1.2. Secondary evaluation variable

There are no secondary variables for efficacy.

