Citospin, Cell Production Unit, Scientific Park of the University of Valladolid, R + D Building, [name]. [contact]. Technical Director: Dra. [name]

Phase of the clinical trial

Phase I-II

Objectives:

Main goal:

□ Evaluate the feasibility and safety of the local use of allogeneic MSV for the treatment of lumbar degenerative disc disease.

Secondary objectives:

□ Evaluate the efficacy of allogeneic MSV treatments using criteria of clinical evolution objectified by the low back pain questionnaires (Visual Scale Analog, VAS), disability (Oswestry questionnaire) and quality of life (questionnaire SF-36 in its abbreviated version, SF-12).

Follow-up of the evolution of disc dehydration by the images of MRI calibrated at T2.
Compare the efficacy of the treatments in the control and experimental arms.

Total number of patients

The number of patients treated will be 24, 12 for each of the branches.

Participating countries

The study will be carried out at the Hospital Clínico Universitario de Valladolid. [name], Spain

Treatment duration

The implantation will be carried out in a single session and the evolution of the patients for 12 months.

Schedule and expected completion date

Start of study: last quarter of 2012

Recruitment: for a maximum of 6 months, until 12 patients are obtained for each branch.

Duration of the trial: 12 months after the treatment of the last patient.

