3.3. Primary Criteria

3.3.1. Radiographic criteria

□ In profile radiography, carried out with the same technical characteristics and hourly (before noon), the height of the space will be measured intervertebral in millimeters, this being the variable that will be compared with measurements that occurred over time (6 and 12 months after implantation of MSV). An increase in height will be understood as rehydration disc associated with an increase in proteoglycans and cellularity of the NP.

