3.3.2 Magnetic Resonance Criteria

□ A quantitative assessment of the water content of the affected segments on T2 images (Sakai et al., 2006; Hiyama et al., 2008; Watanabe et al., 2009), following the procedure below illustrated in Figure 4 (see foot for details) (Orozco et al., 2011). The initial values will be compared with those obtained 6 and 12 months after the intervention.

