3.4. Secondary criteria

□ Clinical observations of the surgeon

□ Evaluation of lumbar pain and general health status according to the Visual Scale Analog (EVA, see Annex V). The score will be transformed to a scale 0-100% for analysis (Huskisson, 1974)

□ Disability assessment using the Oswestry questionnaire (Davidson & Keating, 2002) (ODI, see Annex VI).

□ Assessment of quality of life using the simplified version of the questionnaire Short Form-36 (Davidson & Keating, 2002). It has been shown that this simplification (SF-12; see Annex VII) has a statistical value that approximates much the complete test (Gandek et al., 1998).

4. TYPE OF CLINICAL TRIAL AND DESIGN OF THE SAME 4.1 Type of CT

Phase I-II clinical trial, single-center, prospective, randomized, blinded **, controlled for the treatment of lumbar degenerative disc disease with intact fibrous ring proven by MRI, with two arms: a control arm with placebo treatment (injection of mepivacaine at 1%) and another experimental arm treated with allogeneic MSV. This is the third application of a PEI consisting of Ex vivo expanded bone marrow mesenchymal cells (PEI No. 10-1349). In both cases, the product will be administered in a volume of 2 ml per injection in the nucleus pulposus area.

** Double blind, masked for the patient and evaluators performing the analysis of the results, open to the doctor who applies the cells.

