11.2.1 Main objectives, main variables

- Evaluate the feasibility and safety of the use of allogeneic MSV injected into the disc space for the treatment of lumbar degenerative disc disease and pain and the disability it causes.

The variables that will be used to evaluate safety will be the AAG number related to study medication and the percentage of patients who presented a related AGS. -Evaluate the analgesic-anti-inflammatory efficacy determined by the variation of the Low back pain assessment questionnaire scores (VAS), disability (Oswestry) and health and quality of life (SF12) at 3, 6 and 12 months.

- Evaluate regenerative efficacy using quantitative MRI imaging criteria determined by the appearance of improvements in disc dehydration at 6 and 12 months.

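### Sections 3.3/3.4, 7.1 and 11.2.1 rank the efficacy variables differently, so the lead efficacy result is not fixed in advance

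*Combined protocol and SAP*

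**What the plan says.** The objectives are clear. The main goal in the Summary is "Evaluate the feasibility and safety of the local use of allogeneic MSV", and section 3.1 agrees. Efficacy is a secondary objective in the Summary and in 3.2, and section 3 calls the comparison with control preliminary. Sections 5.4 and 11.1 fix 12 patients per arm on feasibility and safety grounds, with no power calculation.

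The variable lists do not follow from this, and they differ from each other.

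- **Section 3.3 (primary criteria)** names radiographic disc height, "this being the variable that will be compared with measurements that occurred over time", and MRI, "A quantitative assessment of the water content of the affected segments on T2 images", each at 6 and 12 months.
- **Section 3.4 (secondary criteria)** contains "Evaluation of lumbar pain and general health status according to the Visual Scale Analog", together with ODI, SF-12 and the surgeon's observations.
- **Section 7.1.1 (main evaluation variable)** begins "The objective is the evaluation of the efficacy using clinical criteria", names VAS, ODI and SF-12, and adds quantitative MRI. Disc height is absent.
- **Section 7.1.2** reads "There are no secondary variables for efficacy".
- **Section 11.2.1 (main objectives, main variables)** lists safety, then pain, disability and "health and quality of life (SF12) at 3, 6 and 12 months", then "Evaluate regenerative efficacy using quantitative MRI imaging criteria" at 6 and 12 months. Disc height is not in that list, but it is described in 11.2.1.1 beneath the same heading.

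Section 11.2 puts every hypothesis test at two-sided 5% and gives no order, lead visit or multiplicity rule. Section 11.3.7 sends the questionnaire comparisons at 3, 6 and 12 months, and the 12-month proportion with regeneration, to the methods of 11.2.

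**The concern.** If the questionnaires are secondary, section 7.1.2 is wrong. If there are no secondary efficacy variables, section 3.4 is wrong. If disc height is primary, section 7.1.1 is incomplete. These are differences in current text, and a translation or extraction fault does not explain them.

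At stake is which efficacy result is reported as the pre-specified one. From one section or another, an author could present disc height, MRI, VAS, ODI or SF-12 in that role, at more than one visit, after seeing which looked best. The plan does more than describe efficacy: comparing the arms is a stated objective in 3.2, and 11.2 supplies a significance test for it. Moreover, neither 3.3 nor 7.1.1 names a safety variable, although feasibility and safety are the main objective and the reason for the sample size.

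**Working it through.** **Step 1. The rankings side by side.**

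| Variable | 3.3 / 3.4 | 7.1.1 / 7.1.2 | 11.2.1 |
|---|---|---|---|
| Disc height | Primary | Not named | Not in list; described in 11.2.1.1 |
| Quantitative MRI | Primary | Main | Main |
| VAS, ODI, SF-12 | Secondary | Main; no secondary variables exist | Main |
| Safety | Not named | Not named | Main |

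Only the MRI row agrees across the three columns. It does not settle the matter, because MRI shares its rank in each list and is measured at both 6 and 12 months.

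**Step 2. What unordered testing can do.** This illustrates testing at 5% without an order. It does not measure the label conflict: the figure would be the same if every section agreed that the questionnaires were secondary, or that all were main.

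Inputs from the documents: 12 patients per arm (11.1); two-sided 5% per test (11.2); three questionnaires at 3, 6 and 12 months (11.2.1, 11.3.7). Assumptions: 11.3.7 means a between-arm comparison at each visit, each questionnaire gives one score, and the scores are equally correlated. The documents give no correlations.

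- Number of tests: 3 questionnaires × 3 visits = 9.
- If independent: 1 − 0.95^9 = 0.370.
- If correlated: 200,000 null trials were simulated per setting, with 12 per arm and a two-sample t-test on 22 degrees of freedom for each score. The proportion with at least one p<0.05 was counted.

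Annex V and section 5.2.1 also provide for a sciatic pain scale. If lumbar and sciatic VAS are scored separately, there are 4 × 3 = 12 tests; if independent, 1 − 0.95^12 = 0.460.

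| Assumed correlation | 9 tests | 12 tests |
|---|---|---|
| 0.9 | 0.13 | 0.14 |
| 0.7 | 0.21 | 0.24 |
| 0.5 | 0.28 | 0.33 |
| 0.3 | 0.33 | 0.40 |

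For nine tests, the chance that at least one p<0.05 favours MSV is 0.06 to 0.17 over the same range. One named score at one visit gives 0.05, and 0.025 in favour of MSV. With the rank-sum test, which 11.2 also allows, the nine-test range is 0.12 to 0.31.

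Imaging is left out of the count because 11.2.1.1 and 11.2.1.2 specify paired tests against baseline. The 12-month regeneration proportion in 11.3.7 is also left out.

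**The case against.** The strongest reply is that this is a small phase I-II study whose purpose is feasibility and safety. Efficacy is labelled secondary and preliminary, no power is claimed, and MRI is ranked primary or main in every list. On that view the labels hardly matter.

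Much of this stands, and it limits the point to how efficacy is presented. It does not remove the point. The plan still tests efficacy at 5%, and no section identifies a single variable at a single visit.

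A second reply is that the simulation rests on a reading. Section 11.3.7 refers back to 11.2, and 11.3.6 uses the same reference for change from baseline, so the between-arm reading is not certain. That is fair, and the percentages are offered only as an illustration.

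A reader might also infer more conflicts than the text supports:

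- **Section 11.3.2** mentions a secondary efficacy endpoint. This can be read as efficacy being a secondary objective, so it is not counted.
- **Section 5.5** defines non-response with an and/or. Its next sentence defines partial response as improvement of one kind alone, which mostly resolves it.
- **Section 11.3.7** does not define regeneration, but 11.2.1 ties regenerative efficacy to quantitative MRI. Some doubt remains because 3.2 also mentions radiographs.
- **The related-only count of serious adverse events in 11.2.1** might suggest that unrelated events go unreported. Section 11.3.6 tabulates all adverse and serious adverse events, so nothing is hidden, and this is a separate matter.

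**Conclusion.** The inconsistency is real and can be checked from the text alone. VAS, ODI and SF-12 are secondary in one section and main in two others, while a further section denies that secondary efficacy variables exist. Disc height is primary in 3.3, missing from 7.1.1 and from the list in 11.2.1, and back in 11.2.1.1. The lead efficacy result is therefore not fixed.

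For scale, unordered testing of the questionnaires carries about a 13-33% chance of at least one nominally significant result with no true effect (about 14-40% with 12 tests), against 5% for one named test. These figures rest on assumed counts and correlations.

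Two stronger conclusions may tempt a reader. One is that the trial lacks a valid purpose or has failed; the documents state feasibility and safety as the main objective and base the sample size on them, so that does not follow. The other is that 13-33% is the trial's false-positive rate; it is a conditional illustration and no such rate can be derived from the plan. What remains is a risk of a selected efficacy headline, worth correcting because the remedy is cheap.

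**What to change.** Use one ranking in 3.3, 3.4, 7.1, 11.2.1 and 11.3.2, with feasibility and safety as main. Then do one of the following before treatment codes are released to anyone analysing the data:

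- (a) name one efficacy variable, one visit and the between-arm comparison as the lead efficacy result, and label all others, including disc height, as supportive; or
- (b) declare all efficacy exploratory, with no claim based on a single p<0.05.

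The timing is tied to release of the codes because the plan describes its masking in more than one way: evaluators are masked in the Summary and 4.1, but 11.5 leaves blinding beyond the patient for the future.

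In 11.3.7, state that regeneration is judged on the quantitative MRI variable of 11.2.1, or name disc height as well if that is intended.

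The cost is protocol and SAP wording. No new data, visits or patients are needed. The sponsor gives up the later choice of headline.

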7.2 TEST SCHEDULE

VER TABLA EN LA PAGINA SIGUIENTE

CRONOGRAMA	Preinclusión	Inclusión	Tratamiento	Seguimiento (m=meses)			
PROGRAMA DE VISITAS:		V0	Día 1 V1	Día 8 V2	3 m V3	6 m V4	12 m V5
Historia Clínica y Exploración Física	x	x		x	х	x	x
Entrega de la Hoja de Información	x						
RX Columna Lumbar Simple y dinámica	x					x	x
Firma del Consentimiento Informado		x					
Serologías víricas preceptivas		X					
Comprobación de criterios de Inclusión y Exclusión		x					
RM lateral, T2, cuantitativa		x				x	x
EVA, Oswestry, SF-12		X			х	x	x
Tratamiento control o con MSV alogénicas*			**X				
Analítica Control		x		x		x	x
VISITA:		0	V1	V2	V3	V4 M	V5 12 M

* Las MSV deben haberse obtenido del donante y expandido en la ventana temporal adecuada. **RX en quirófano para guiar y seguir aplicación. La RM de Vo se usará también

para valorar la integridad del anillo fibroso externo.

7.2.1. Visiting Program

Pre-Inclusion: In patients who come for consultation and whose medical history and examinations complementary, including X-rays and / or MRI, presume an orientation diagnosis with the possibility of inclusion in the trial, presenting all the criteria of inclusion and none of exclusion, the treatment regimen will be prescribed according to the standard and then they will be informed of the possibility of inclusion in the EC. They will deliver the "Patient Information Sheet" (Annex II) and, if its decision is affirmative, Inclusion procedures will begin on a future visit.

Visit 0. Inclusion. May comprise more than one physical visit. If the patient confirms that want to join the trial, you will be asked to sign the "Consent Document Informed "(Annex II). You will be ordered new MRI and radiographic scans with the mandatory characteristics of the study unless these examinations had already been performed previously within a period of no more than 6 months. Completed analytics will be requested with the regulated serology for determination of HIV, Hepatitis and Lúes and test of pregnancy if you are a woman of childbearing age. Although positive serology is not a reason for exclusion in this trial, it will be done for epidemiological reasons. After checking the inclusion and exclusion criteria, the clinical history will be made, including data referring to low back pain and discopathy, treatments carried out, analytics and imaging tests to define the characteristics of the same and carry out the measurements that will be taken as a standard of future explorations. Low back pain evaluation questionnaires will be passed (VAS), disability (Oswestry) and quality of life (SF-12). It will be scheduled on the day of the intervention (V1) and the X-ray and MRI tests will be performed, if they had not already been performed.

Visit 1 (day 1). Placebo injection or allogeneic MSV, depending on the clinical trial arm. Visit 2 (8 days): Safety assessment. Includes analytical control.

Visit 3 (3 months): Safety assessment. EVA, Oswestry and SF-12 questionnaires. RX. Visit 4 (6 months): Safety assessment. EVA, Oswestry and SF-12 questionnaires. RX. RM.

Visit 5 (12 months) Safety assessment. EVA, Oswestry and SF-12 questionnaires. RX. RM.

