4.2 Overall study design

The study consists of 2 arms, one experimental with allogeneic MSV, and another control in the to be injected into the area of the paravertebral muscles near the injury saline serum containing 1% mepivacaine (1 ml of 2% mepivacaine + 1 ml of saline) in identical volume and subject to the same maneuvers as the intervention on the arm experimental. Participants in the study will be offered the possibility of, once completed the study, receive MSV treatment if it proves beneficial and the patient so wishes. The inclusion criteria in both arms are identical, but after recruiting patients will be randomly assigned to one of the treatments. The Cell manufacturing will be carried out by Citospin at the facilities of the Park Scientist of the UVa and the application and monitoring will be carried out at the Clinical Hospital University of Valladolid. 24 patients diagnosed with low back pain and / or low back pain attributable to disc degeneration and evidence of proven continuity of the external fibrous ring in the magnetic resonance image. The patients will be evaluated clinically, by the previous imaging studies (X-ray and MRI). If they are considered inclusive, they will be provided with the information regarding the clinical trial and the "Patient Information Sheet" (Annex II), citing them for the Inclusion visit. In the "Inclusion Visit", if the patient decides to participate in the trial, they must sign the "Informed Consent Document" and a visit will be scheduled for the practice of MRI and radiographs, which will be considered the pattern on which the possible determinable changes in the controls at 6 and 12 months. If you are MRI and X-rays have been recently performed and their characteristics are valid for the study, its repetition can be avoided. In this visit, basic analytics will also be requested, serology for HIV, lues and hepatitis B and C, and a serum sample will be obtained that will be sent to the Cell Production Unit for filing in the Seroteca. Although the Positive serology is not a criterion for exclusion of the recipient in the present test, it will be performed for epidemiological and preventive purposes. At the next visit (V0), it will be verified that all the inclusion criteria persist and that no exclusion is presented and the patient will be randomized (blind for him) in one of the two treatment groups and the date of implantation of MSV (V1). Once the mobile application is made, the patients will be followed up safety and to determine efficacy as established in the visit program (V2 to V5, see later).

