5.3.2. Exclusion criteria

• Any criteria for non-compliance with the inclusion criteria

• HIV or Hepatitis positive

5.3.3 Procedure:

It is described in detail below (section 6.1). In essence, in the Eudra CT2009-017405-11 usually starts with 80-100 ml of bone marrow. The mononuclear cells and is selected by adherence to the plastic in T-175 bottles. Depending performance, which is highly variable depending on the patient, is obtained in this phase between 6 and 45x106 adherent cells, which expand about 10 times in the following 3 weeks for use in the clinical trial. Taking into account that the required number of MSV is of about 80x106 cells, in some patients there is a significant surplus of cells in this stage. It is proposed here to start between 1 and 5 additional expansion batches (depending on the number of cells obtained) for use in the present clinical trial. The details of the protocol are discussed in section 6.1.

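### The only pregnancy test named is at V0, with no check named at V1 and no limit on the V0–V1 interval, so the result may be out of date at the injection

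*Combined protocol and SAP*

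**What the plan says.** Pregnancy or breastfeeding is exclusion 7 in section 5.1.2. Patients aged 18 to 75 can enter, so women of childbearing age are eligible.

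The pregnancy test appears in the Visit 0 entry of section 7.2.1, among the laboratory requests: "test of pregnancy if you are a woman of childbearing age". Section 4.2 states that at V0 "it will be verified that all the inclusion criteria persist and that no exclusion is presented and the patient will be randomized", and the date of V1 is set at that point. In the 7.2 table the row for checking the criteria ("Comprobación de criterios de Inclusión y Exclusión") is marked at V0 only.

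The whole Visit 1 entry in 7.2.1 reads "Visit 1 (day 1). Placebo injection or allogeneic MSV, depending on the clinical trial arm". A table footnote to the treatment cell adds X-ray in the operating room: "RX en quirófano para guiar y seguir aplicación". Section 6.1.3 describes light sedation, fluoroscopy and the puncture. Section 4.2 gives controls the same handling, and section 8.2 counts sedation among the risks of both injections.

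**The concern.** A pregnancy test describes the day on which it is taken. The sponsor decided both to exclude pregnancy and to test for it, so the result should still be current when the exposure happens. Here the exposure is at V1: sedation and X-ray guidance in both arms, and allogeneic cells in the experimental arm.

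The test is tied to V0, and nothing in the visible text ties V0 to V1. A site could follow the schedule exactly and still treat a woman on the strength of an old negative result. Safety is the trial's main objective. No endpoint, comparison or analysis is affected; what is at stake is the protection of an individual patient.

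**Working it through.** The plan states no figure on this point, so there is none to reproduce. The check is to set the sections side by side in time order.

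1. **When the test is done.** It is requested within Visit 0, which 7.2.1 allows to be spread over several attendances. The sample may therefore already be older than the recheck made at randomisation.
2. **What the recheck adds.** The section 4.2 recheck takes place at V0, while V1 is still being scheduled. It names no repeat test, so it cannot detect a later conception.
3. **What is named at V1.** The 7.2.1 entry names the injection. In the 7.2 table the V1 column carries only the treatment; control laboratory tests are marked at V0, V2, V4 and V5. The injection procedure in section 6.1.3, repeated in Annex I, goes from antibiotic prophylaxis to sedation, fluoroscopy and puncture without mentioning pregnancy status.
4. **What limits the interval.** Three time conditions might seem to do so, and none does.
   - The Visit 0 entry asks for new imaging "unless these examinations had already been performed previously within a period of no more than 6 months". That sets an age limit for images; the same paragraph sets none for the pregnancy result.
   - The 6 months in the section 1 summary is the recruitment period.
   - The table footnote "Las MSV deben haberse obtenido del donante y expandido en la ventana temporal adecuada" concerns the cell product, and its adequate window has no number.
5. **How long the interval might be.** Section 6.1.1 gives 3–4 weeks for culture, that is 21–28 days (3 × 7 to 4 × 7). This would be the wait only in the cell arm, and only if culture started after randomisation. Section 5.3.3 foresees "between 1 and 5 additional expansion batches" from surplus donor cells, so a batch may already be under way, and controls need no cells. The interval could be shorter, and nothing stops it being longer.
6. **Who could be missed.** A recognised pregnancy would be caught by exclusion 7, or by the investigator's power under section 5.6 to withdraw a patient for her benefit. What remains is a pregnancy that began after the V0 test, or was too early to show on it, and is unrecognised at V1.
7. **Whether that can be quantified.** A probability would need the number of women of childbearing age among the 24 patients, a conception rate and the V0–V1 interval. The documents give none of the three.

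**The case against.** The strongest defence is that silence at V1 proves little. The 7.2.1 entry for that visit is a one-sentence label that also leaves out prophylaxis and sedation, which section 6.1.3 requires. The 7.2 table is not exhaustive either: it has no pregnancy-test row even at V0, where the test is ordered. Annex I sends the patient through outpatient admission procedures whose content is not given. The patient information and consent pages in Annex II were not available, and an instruction on contraception, or on telling the team about a possible pregnancy, would naturally sit there.

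Much of this stands. A reader might infer that the plan contains no safeguard at all after V0, or that it omits contraception. The documents support neither inference; the most that can be said is that no step is named in the visible text. The defence does not remove the point, though. Section 6.1.3 and Annex I describe the day's procedure in detail, beyond any label, and neither mentions a check. A contraception instruction would lower the risk, but it would not be a test before exposure.

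It is also fair to say that the existing protections leave only a small residual, and that a second test narrows it without closing it, since a conception in the last few days cannot be detected.

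**Conclusion.** The point holds in a limited form. One pregnancy test is named, at V0; eligibility is rechecked only at V0; no check is named at V1; and the V0–V1 interval has no limit. The V0 result may therefore be out of date when the patient is sedated, X-rayed and injected.

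The residual risk is low and cannot be quantified from the documents. Two further inferences should be resisted. One is that every patient waits 3–4 weeks: that is a culture time, it need not equal any patient's wait, and it does not apply to controls. The other is a percentage risk: any such figure would rest wholly on assumed inputs, and with an open-ended interval it would not bound the risk either.

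The conclusion assumes that the visible visit schedule and injection procedure are what a site would follow, and it is subject to whatever the consent pages and local admission procedures contain. The case for change rests on how little it costs to close a plain gap in a trial whose main objective is safety. This is a worthwhile improvement to the schedule; it is not a flaw in the trial's inference.

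**What to change.** Add to the Visit 1 entry of section 7.2.1, for both arms:

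> Women of childbearing age: a negative pregnancy test shortly before V1 (for example within 72 hours, same day allowed, preferably before the dose is packed) is required before sedation and fluoroscopy. If positive, do not treat, and replace the patient in the same group under the existing replacement rule.

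Add a pregnancy-test row to the 7.2 table, marked at V0 and before V1. The 72 hours is a suggestion; the documents do not favour one short window over another. The replacement rule is already in section 5.6, so no new procedure is needed for a positive result.

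The cost is one sentence, one table row and one routine test per woman of childbearing age. No extra visit is needed, because the day of V1 is allowed. Rarely, a positive result means a late cancellation. If the dose has already been packed it may be wasted, since Annex I requires the cells to be used within 12 hours of packing; testing before packing limits that loss. Endpoints, sample size and analysis are unchanged.
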